 - ii. Moderate-to-severe persistent asthma, defined by the National Heart, Lung, and Blood Institute. This will be done by a physician-trained RA who will be able to identify potential participants prior to recruitment.
 - iii. At least one asthma exacerbation that required a course of oral corticosteroids in the past year
 - iv. Prescription and utilization of an ICS inhaler for at least the past year.
 - v. Who are seen at: Clark and Deming Resident Clinic, Lurie Children's Pulmonary Clinic, Lurie's Uptown Clinic or Chicago Healthcare Associates
- b. Exclusion criteria:
 - i. Non-English speaking parents/families
 - ii. Patients seen in the hospital who receive primary care outside of the study's clinics
 - iii. Children with any comorbid conditions, which interfere with appropriate assessment of asthma symptoms: Chronic Lung Disease, Broncho-Pulmonary Dysplasia, Cystic Fibrosis, Pulmonary Hypertension, Interstitial Lung Disease, Immunodeficiency, Bronchiectasis, Primary Ciliary Dyskinesia, Chronic Respiratory Insufficiency, Neuromuscular Weakness, Sickle Cell Lung Disease, Restrictive Lung Disease, and Tracheostomy or Ventilator-dependence
 - iv. Child-patients who are participating in any other research studies that would interfere with our ability to use and track the inhaler sensor

3. Pilot Phase

- a. 10 children and their families will be recruited by their healthcare provider to join this study for 30 days. After enrollment, participants in the pilot phase will receive the Remote Health Management device, as well as the same training and education that the Intervention group will receive, including the allergen testing.

Enrollment: Informed consent will be obtained at the time of enrollment. Families in the Intervention arm will receive Remote Health Management sensors. Data collected at the time of enrollment will include the following for each participant:

- a. Basic demographic and clinical history data (obtained by a review of medical records)
 - a. Include: name, date of birth, date of asthma diagnosis, zip code, history of a course of oral corticosteroid, current medications, phone call/email history to the clinic, asthma exacerbation history, and history of asthma-related ED visits and hospitalizations.
- b. Parent questionnaires, including the Asthma Control Test (ACT), Parental Asthma Management Self Efficacy (PAMSE) scale, intervention survey, and the Pediatric Asthma Caregiver's Quality of Life Questionnaire (PACQLQ).

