- b. Health providers will be interviewed about their experience using the web portal (Study Aim 3), using the data generated by the sensors, and managing pediatric asthma patients and their interaction with parents
- e. Health providers will be informed that the in-person, or telephone, interview will be audio-recorded. In-person interviews will be conducted at their clinic location in a private office.
- f. Interviews will last approximately 60 minutes and conducted by research staff.

Study Extension

Data analysis will begin 12 months after a participant is enrolled (beginning January 2018.). During the analysis period, we will also determine the feasibility of implementing the intervention more broadly throughout the healthcare system.

Study Subjects:

Eligible participants will be children 4-17 years old with moderate or severe persistent asthma, as diagnosed by their pediatrician, who are primarily seen for their asthma care at one of the participating clinical sites, and who have parents/caregivers willing to participate in this study. Participants will also be required to have received oral corticosteroids in the past year.

Study Enrollment:

Recruitment will occur by a research assistant at all sites. Scheduling of recruitment and participant screening will require the healthcare team to identify potential participants and then the RA either calling or mailing an informational pamphlet to the parents prior to their next appointment. Participants may also be recruited in the clinic by the RA, but will require the RA to follow-up with them via the telephone to properly install and utilize the Remote Health Management Platform. Participants may also be recruited through Lurie Children's Hospital Inpatient service after an asthma exacerbation. Only children who receive their primary care from one of the 5 study clinics will be permitted to be in the study. A member of the research team will work with hospitalists to recruit these individuals.

For the post-trial semi-structured interviews, only those participants who had previously responded that they were interested in further contact by the research team will be recruited. Study staff will contact potential participants for interviews by telephone and only schedule a time if participants remain interested after the interview study has been explained to them.

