| Parent-reported values (un-validated) | School days missed due to asthma | 5 times in total (baseline, 3 months, 6 months, 9 months, study completion) |
| Pediatric Caregiver Asthma-related Quality of Life Questionnaire (PACQLQ) | Parent form of how their child's asthma is affecting both their lives and the life of their child | 5 times in total (baseline, 3 months, 6 months, 9 months, study completion) |

Parental Management Outcomes

| Source | Outcome | Time Point |
|-----------------------------------|--|---|
| Parent report (Survey) | Feasibility and acceptability of Platform | 5 times in total (baseline, 3 months, 6 months, 9 months, study completion) |
| Remote Health Management Platform | Frequency of use of the application (synching) | Monthly data pull |

Physician and Clinical Team Outcomes

| Source | Outcome | Time Point |
|-----------------------------------|---|---|
| Remote Health Management Platform | ICS and SABA use | Monthly download |
| Web Portal/Epic | Asthma-related ED visits, hospitalizations, and oral corticosteroid prescriptions/courses | Monthly Epic data pull |
| Clinician Survey | Feasibility and acceptability of the Platform | 1 month into the study, 6 months and study completion |
| Physician Survey | Feasibility and acceptability of the Platform | 1 month and study completion |
| Remote Health Management Platform | Frequency of use of the web portal | Monthly data pull |

Data Analysis:

Primary Outcomes

- *ACT*: Parent-reported test on their child's asthma control
- *Asthma-related hospitalizations*: Data will be obtained from the EMR and parent report.
- *Asthma-related ED visits*: Data will be obtained from the EMR and parent report.
- *Asthma-related oral corticosteroid use*: Prescription/course data will be obtained from the EMR and parent report.

Secondary Outcomes

- *Inhaler Use*: Use data, including frequency of both SABA and ICS inhalers, will be obtained via the sensor throughout the study period.
- *PAMSE*: Parental Asthma Management Self-Efficacy; self-report survey that measures parental self-efficacy for the management and prevention of acute exacerbations of asthma.
- *PACQLQ*: Paediatric Asthma Caregiver's Quality of Life Questionnaire; will assess the impact of their child's asthma on their lives, the lives of their children with asthma, and the family as a whole.

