Clinical and psychological outcomes of interest include the 12-month rate of asthma-related oral corticosteroid use, ED visits, and hospitalizations, as well as change in mean ACT scores (range of 0 to 27) from baseline to end line (12 months). Psychological outcomes of interest include quality of life score (range of 1 to 7), parental self-efficacy score, and the number of school days missed due to asthma. Potential predictors of outcomes include age (4 to 7 years vs. 8 to 17 years), gender (M vs. F), race/ethnicity (non-Hispanic white, non-Hispanic Black, Hispanic, vs. others), insurance status (private/public), and co-morbidities.

Each count variable (asthma-related oral corticosteroid use, ED visits, and hospitalizations) will be analyzed by mixed negative binomial regression analysis adjusting for treatment, all potential predictors, and including maximal random effect structures (i.e., slope and intercept as allowed by the model) of family and clinic. VIFs (variance inflation factors) will be computed for each predictor. Highly correlated predictors (i.e. predictors that can be well-explained by other predictors) will be dropped from the model to avoid multicollinearity issues. Model fit criteria, parameter estimates, and precision of parameter estimates will all be evaluated to select the most parsimonious model.

For each continuous primary outcome variable (i.e., ACT score), change-from-baseline score at each visit will be analyzed using mixed linear regression models, adjusting for treatment, time point, baseline score, all potential predictors, and including random effects (i.e., both slope and intercept) of family and clinic. A treatment by time interaction will be included to evaluate whether the effect of the treatment on the primary outcome varies by time point. VIFs will be investigated for each predictor, and those with high VIFs ($VIF \geq 10$) will be dropped from the model to avoid multicollinearity issues. An unstructured covariance (UN) matrix will be assumed. Model fit criteria, parameter estimates, and precision of parameter estimates will also be used to select the most parsimonious model.

Model diagnostics will be performed to check model assumptions. All analyses will be performed using statistical analytic software Stata Version 15.1.

AIM 2. Enhance parental management through improved inhaler use.

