4. In the past week, how many alerts did you receive due to patients overusing albuterol?
 - One
 - Two

- 3 or more
- 5. In the past week, how many times did you have to follow-up with patients regarding their underuse of their controller medication?
 - Once
 - Twice
 - 3 or more times
- 6. In the past week, how many alerts did receive due to patients underusing their controller medication?
 - One
 - Two
 - 3 or more
 - Zero
- 7. On a scale of 1-5 (1 being the least helpful, and 5 being the most helpful), how helpful do you feel calls to patients improve asthma management?
 - 1
 - 2
 - 3
 - 4
 - 5
- 8. On a scale of 1-5 (1 being the least useful, and 5 being the most useful) how much do you think the parents found your call useful?
 - 1
 - 2
 - 3
 - 4
 - 5

Qualitative Questions:

1. What do you find useful about the Propeller dashboard?
2. What changes do you think are needed to improve the Propeller dashboard?
3. How are you currently using the Propeller dashboard? Please describe.
4. Would you utilize the Propeller health management platform for your current practice in the future?

Sample Size Determination:

Assuming asthma exacerbation rate of 0.545 for the intervention arm, and asthma exacerbation rate of 0.75 for the standard treatment arm, resulting odds ratio (OR) equal to 0.3992674, and $\log(\text{OR}) = -0.9181239$. Assuming 20% patient drop-out rate, two-sided significance level $\alpha = 0.05$, a total of 250 patients (125 per arm) is needed in order to achieve a statistical power of 85%. The sample size calculation was computed using SAS procedure PROC SEQDESIGN.

Qualitative Analyses of Semi-Structured Interviews:

Data will be analyzed systematically using a constant comparative approach; and four analysts (i.e., coders), including [name] (qualitative methods expert), [name], and 2 research team members, will meet to discuss initial thoughts, insights, and observations for the development of initial coding categories (e.g., themes). Through a systematic analysis process, themes will be continually refined by collapsing redundant themes and removing irrelevant themes. Once no new categories have emerged, a

codebook will be developed for the remaining analysis. We will construct a saturation grid, to track themes as they emerge and determine when no new information is obtained

Study Staff:

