# AIM 1. Determine factors influencing clinical and psychosocial outcomes.

Clinical and psychological outcomes of interest include the 12-month rate of asthma-related oral corticosteroid use, ED visits, and hospitalizations, as well as change in mean ACT scores (range of 0 to 27) from baseline to end line (12 months). Psychological outcomes of interest include quality of life score (range of 1 to 7), parental self-efficacy score, and the number of school days missed due to asthma. Potential predictors of outcomes include age (4 to 7 years vs. 8 to 17 years), gender (M vs. F), race/ethnicity (non-Hispanic white, non-Hispanic Black, Hispanic, vs. others), insurance status (private/public), and co-morbidities.

Each count variable (asthma-related oral corticosteroid use, ED visits, and hospitalizations) will be analyzed by mixed negative binomial regression analysis adjusting for treatment, all potential predictors, and including maximal random effect structures (i.e., slope and intercept as allowed by the model) of family and clinic. VIFs (variance inflation factors) will be computed for each predictor. Highly correlated predictors (i.e. predictors that can be well-explained by other predictors) will be dropped from the model to avoid multicollinearity issues. Model fit criteria, parameter estimates, and precision of parameter estimates will all be evaluated to select the most parsimonious model.

For each continuous primary outcome variable (i.e., ACT score), change-from-baseline score at each visit will be analyzed using mixed linear regression models, adjusting for treatment, time point, baseline score, all potential predictors, and including random effects (i.e., both slope and intercept) of family and clinic. A treatment by time interaction will be included to evaluate whether the effect of the treatment on the primary outcome varies by time point. VIFs will be investigated for each predictor, and those with high VIFs (VIF>=10) will be dropped from the model to avoid multicollinearity issues. An unstructured covariance (UN) matrix will be assumed. Model fit criteria, parameter estimates, and precision of parameter estimates will also be used to select the most parsimonious model. Model diagnostics will be performed to check model assumptions. All analyses will be performed using statistical analytic software Stata Version 15.1.

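### The stated 85% power belongs to a two-proportion odds-ratio test of asthma exacerbation, not to the planned analysis of any primary outcome, and at least three of the four primary outcomes have no planning assumption

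*Protocol*

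**What the plan says.** The only sample size statement in the text available for review is the protocol's Sample Size Determination section. It opens with "Assuming asthma exacerbation rate of 0.545 for the intervention arm, and asthma exacerbation rate of 0.75 for the standard treatment arm". The effect measure that it derives from these two figures is given as "resulting odds ratio (OR) equal to 0.3992674". With a two-sided alpha of 0.05 and 20% drop-out, it concludes that "a total of 250 patients (125 per arm) is needed in order to achieve a statistical power of 85" percent. It gives no time window and does not say which listed outcome an exacerbation is.

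The protocol's Data Analysis section lists four primary outcomes: ACT, asthma-related hospitalizations, asthma-related ED visits and asthma-related oral corticosteroid use. For the last of these, "Prescription/course data will be obtained from the EMR and parent report".

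Under Aim 1 the protocol says "Each count variable (asthma-related oral corticosteroid use, ED visits, and hospitalizations) will be analyzed by mixed negative binomial regression analysis", and the SAP plans the same. For ACT the SAP says "For each continuous primary outcome variable (i.e., ACT score), change-from-baseline score at each visit will be analyzed using mixed linear regression models". Both models carry family and clinic random effects. Neither document plans a binary or odds-ratio analysis of a primary outcome.

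**The concern.** A sample size statement should tell the reader how likely the planned primary analysis is to detect a stated effect. Here the outcome that was sized is not on the primary list, and the test that was sized is not in the analysis plan. The reader cannot tell which of the four primary outcomes the 85% is meant to protect.

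The word used for 0.545 and 0.75 adds to the problem. The sample size section calls them rates, and Aim 1 uses the same word for the 12-month count outcomes, yet an odds ratio can only be formed from them if they are proportions. For the outcomes with no event rate, dispersion, SD or target difference, no detectable effect was fixed in advance, so a null result has no planned effect size to be set against.

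**Working it through.** **1. Reproduce the plan's figure.** Inputs from Sample Size Determination: p1 = 0.545, p2 = 0.75, two-sided alpha 0.05 (z = 1.960), power 85% (z = 1.036), drop-out 20%.

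- OR = (0.545/0.455)/(0.75/0.25) = 0.3992674; ln OR = -0.9181239. Both match the protocol.
- Variance term: 1/(0.545 × 0.455) + 1/(0.75 × 0.25) = 4.033 + 5.333 = 9.366.
- n per arm = (1.960 + 1.036)² × 9.366 / 0.9181² = 99.76, so 100 evaluable.
- 100/0.80 = 125 per arm, 250 in total. Power at 100 per arm is 85.1%.

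Other two-sided 85% formulas give different totals: 240 (pooled proportions), 266 (with continuity correction), 236 (unpooled risk difference). The 85% therefore belongs to an unpooled Wald test of a log odds ratio between two proportions.

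**2. Does it carry over to a count comparison?** The documents give no dispersion, so these are illustrations. All use 100 evaluable per arm, one full year of follow-up, no covariates and no random effects. Power = Φ(|ln RR|/SE − 1.960).

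*(a) Proportions with at least one event, common negative binomial dispersion k in both arms.* The mean implied by p is m = ((1−p)^(−k) − 1)/k, or −ln(1−p) at k = 0. SE² = (1/m1 + 1/m2 + 2k)/100.

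| k (assumed) | means | rate ratio | power |
|---|---|---|---|
| 0 | 0.787 vs 1.386 | 0.568 | 98.0% |
| 0.5 | 0.965 vs 2.000 | 0.482 | 99.6% |
| 1 | 1.198 vs 3.000 | 0.399 | 99.9% |

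*(b) The same proportions, but equal mean events μ per affected child in both arms.* The rate ratio is then 0.545/0.75 = 0.727, ln RR = −0.319. If an affected child has one event plus a Poisson number with mean μ − 1, then SE² = [((μ² + μ − 1)/μ²)(1/0.545 + 1/0.75) − 2]/100.

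| μ (assumed) | SE | power |
|---|---|---|
| 1.5 | 0.1368 | 65% |
| 2 | 0.1400 | 63% |
| 2.5 | 0.1389 | 63% |

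*(c) Mean 12-month event rates.* The rate ratio is again 0.727. SE² = (1/0.545 + 1/0.75 + 2k)/100 = (3.168 + 2k)/100.

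| k (assumed) | power |
|---|---|
| 0 | 43% |
| 0.5 | 35% |
| 1 | 29% |
| 2 | 22% |

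**3. Which primary outcome could exacerbation be?** Some text points to oral corticosteroid use. Inclusion Criteria require "At least one asthma exacerbation that required a course of oral corticosteroids in the past year", which Study Subjects restates as "Participants will also be required to have received oral corticosteroids in the past year". The follow-up sections ask caregivers about acute exacerbations where the Clinical Outcomes table lists oral corticosteroid courses. Other text separates the two. Enrollment/Visit 1 lists corticosteroid course history and exacerbation history as different items. The Timeline (Phase 2) has exacerbations as a survey item and takes oral corticosteroid use from the EMR. The link is an inference.

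**4. What 100 per arm could detect at 85% power where no assumption is given.** For a count with control rate m, solve |ln RR| = (1.960 + 1.036) × √((1/(m·RR) + 1/m + 2k)/100). All rates and k are assumed.

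| control rate per child-year | detectable RR, k = 0 | detectable RR, k = 1 |
|---|---|---|
| 0.3 | 0.34 | 0.29 |
| 0.5 | 0.47 | 0.41 |
| 1.0 | 0.62 | 0.51 |

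For ACT, a simple two-mean comparison gives 2.996 × √(2/100) = 0.42 SD.

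**The case against.** Sizing a trial on one outcome with a simpler test than the final model is common, and the arithmetic here is sound. Exacerbation may well be shorthand for an oral corticosteroid course. The illustrative figures rest on inputs the documents do not supply, and they are not the power of the planned models. For example, the 0.42 SD for ACT ignores baseline adjustment and repeated visits; with an assumed baseline correlation of 0.5, a single adjusted visit gives 0.42 × √(1 − 0.25) = 0.37 SD. A null result would still come with a confidence interval showing which effects are excluded. The SAP also plans multiple imputation, so the number analysed may differ from 100 per arm.

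All of that stands, and it keeps the point to one of reporting. It does not remove the mismatch: even if exacerbation means oral corticosteroid use, the model differs and three outcomes have no assumption.

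Two stronger readings are tempting. A reader might infer from (c) that the trial is underpowered, but the printed odds ratio shows that the calculation treated the figures as proportions. A reader might instead infer from (a) that a count analysis must do better than 85%. That result needs a common dispersion in both arms, which enlarges the implied effect; in (b) the same proportions give 63% to 65%. The documents support neither inference.

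**Conclusion.** The point holds as a mismatch that should be fixed. The protocol's 85% is the power of a test that the plan does not contain, for an outcome that is not listed as primary, so it cannot be quoted as the power of any planned primary analysis. At least three of the four primary outcomes lack a planning assumption in the text available for review; read literally, all four do.

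The direction of any difference from 85% is undetermined. The illustrations give 98% to 99.9%, 63% to 65%, or 43% to 22%, according to how 0.545 and 0.75 are read and what is assumed about repeat events. The documents do not show that 250 patients is too few or more than enough. Confidence is high on the mismatch and on the reproduced arithmetic. It is lower on whether exacerbation was meant as oral corticosteroid use.

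**What to change.** Keep the 250 patients, the four primary outcomes and the planned models. In Sample Size Determination:

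1. Name the primary outcome and the time window that 0.545 and 0.75 describe, and say whether they are proportions of children with at least one event or mean event rates.
2. State that 85% applies only to the two-proportion log-odds-ratio comparison. As the trial's stated power, replace it with the power of the planned negative binomial model for that outcome over a stated range of dispersion.
3. For each remaining primary outcome, give the rate ratio or mean difference detectable with 100 evaluable per arm and show the assumptions, or state that the trial was not sized for it.

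The cost is a short calculation and a few sentences. Event rates, dispersions and an SD for ACT have to be sourced or assumed, because the documents do not give them. The downside is that the stated power or detectable effect may look less favourable, especially for rare events.

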- Proventil HFA
- Ventolin HFA
- Xopenex

Supported Controller/Daily Medications:

- Advair HFA
- Advair Diskus
- Asmenex
- Combivent Respimat
- Dulera
- Flovent Diskus
- Flovent HFA
- QVAR
- Serevent Diskus
- Spiriva Respimat
- Striverdi Respimat

Timeline

Pilot: November 2016

- Pilot group of 8-10 families

Phase 1: Enrollment

- December 2016-December 2017
- Collect EMR data from the previous year
- Randomization

Phase 2: Intervention

- December 2016-December 2018
- Intervention Group will have the Remote Health Management device for 1 year
- Standardized Group will receive enhanced, standardized asthma education
- Each group will fill out the following surveys 5x during the study period:
 - ACT
 - PAMSE
 - PACQLQ
 - iTRACC Survey (Control Arm) or Intervention Survey (Intervention Arm)
 - Number of hospitalizations, ED visits, exacerbations
- We will pull information from the EMR to determine oral corticosteroid use

Phase 3: Analysis

- January 2018- December 31, 2018
- All data analyzed
- Preparation and submission of academic abstracts and papers

- Help to prepare for full scale rollout, if applicable
- Semi-structured interviews of subsample of participants
- Semi-structured interviews of health providers in the trial
